2.5 Subject Replacement

Drop-out definition: Any participant who reports significant adverse effects, are unable tolerate the session, or withdraw from the study will be considered drop-out.

Subjects who drop out will not be replaced.

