3 STUDY DESIGN

Figure C: Study Design

At baseline (week 0), all patients will do a one-week sleep actigraphy and complete SDSC questionnaire. At week 1, patients will be randomised to one of the 4 treatment regimen that is determined by the first period of the sequence they are assigned to. Re-evaluation with sleep actigraphy and SDSC questionnaire will be done at week 4, 6 and 10. At week 7, the patients will cross over to the treatment for the second period of the sequence they are assigned to. Over the 10-week period, sleep diary will also be completed daily.

10 patients will receive dose-appropriate Melatonin over 8 weeks (Group A), 10 patients will receive 40 sessions of home-based tPCS over 8 weeks (Group D), 10 patients will receive 4 weeks of Melatonin then cross over to receive 4 weeks of 20 sessions of home-based tPCS (Group B) and 10 patients will receive 4 weeks of 20 sessions of home-based tPCS then cross over to receive Melatonin over 4 weeks (Group C).

There will be a washout period of 2 weeks (week 5 and 6) between cross over. Those on a Melatonin group cross over will also go through the same washout period.

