3.4.2 Discontinuation Visit and Procedures

Subjects may withdraw voluntarily from participation in the study at any time. If withdrawal occurs, subjects will still be asked to complete a questionnaire to study the reason for withdrawal. Actigraphy will be done (if any) to the point of withdrawal from participation in the study.

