8 SAMPLE SIZE AND STATISTICAL METHODS

8.1 Determination of Sample Size

In an inequality test on data from the Balaam's crossover design, a sample size of 32 achieves 83% power at a 5% significance level when the absolute difference between the two treatment means is 0.2 and the within-subject standard deviation is 0.15. To account for 20% drop-out rate, a sample size of 40 (10 in each arm) is required.

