8.2 Statistical and Analytical Plans

The SPSS® 25.0 software (IBM, Armonk, New York, United States) will be used, with statistical significance defined as a p-value of <0.05 . Independent t-tests will be conducted to compare differences in outcomes between the two treatment groups; Wilcoxon signed-rank test will be used to compare continuous variables at start and end of treatment. Average of actigraphic measurements were used to compare effects of treatment on sleep parameters. One-way Repeated Measure ANOVA will be conducted to assess changes in outcomes and patient scores within the group across the timepoints. Non-parametric testing will also be conducted to observe for significant differences in patient outcomes within the groups at each timepoint.

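### The one-way repeated-measures ANOVA for within-group change in section 8.2 drops any child missing one of the four recordings, so it discards valid data from expected drop-outs; a mixed model in the same software would use them.

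*Protocol*

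**What the plan says.** The protocol fixes the method for change over time in section 8.2: "One-way Repeated Measure ANOVA will be conducted to assess changes in outcomes and patient scores within the group across the timepoints".

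Section 3 sets the measurement times: "At baseline (week 0), all patients will do a one-week sleep actigraphy and complete SDSC questionnaire", and then "Re-evaluation with sleep actigraphy and SDSC questionnaire will be done at week 4, 6 and 10". A child who completes the study therefore has four recordings.

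On drop-out:
- Section 8.1: "To account for 20% drop-out rate, a sample size of 40 (10 in each arm) is required".
- Section 2.5: "Any participant who reports significant adverse effects, are unable tolerate the session, or withdraw from the study will be considered drop-out", and "Subjects who drop out will not be replaced".
- Section 3.4.2: "Actigraphy will be done (if any) to the point of withdrawal from participation in the study".

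Section 8.2 also names two other analyses. Independent t-tests compare the treatments, and a Wilcoxon signed-rank test compares values at the start and end of treatment.

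**The concern.** A one-way repeated-measures ANOVA works on complete rows. A child with weeks 0 and 4 recorded who leaves during washout or period 2 contributes nothing to it, although section 3.4.2 keeps those recordings. The protocol thus expects partial records and fixes a method for change over time that cannot use them.

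Two things are at stake in this analysis. One is precision, which is lost even when drop-out is unrelated to response. The other is bias. Section 2.5 defines drop-out through adverse effects, intolerance and withdrawal, and families are not blinded, so those who finish ten weeks may not be a random subset. If children whose sleep improved less are more likely to leave, the change estimated from completers is too large.

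**Working it through.** **Inputs from the protocol.** Four time points (section 3). 32 children needed, 20% drop-out, 40 enrolled, within-subject SD 0.15 (section 8.1). Four sequence groups of 10, hence 20 children on each treatment in period 1 (section 3).

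**The plan's own figure.** 32 / (1 − 0.20) = 40, as stated. Expected drop-outs: 0.20 × 40 = 8, or 2 of 10 per sequence group if spread evenly.

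**Complete-row requirement.** A standard repeated-measures ANOVA routine (Python statsmodels, not SPSS) was given 10 children and four time points, with 2 children lacking the last two. It refused the data as unbalanced. On the 8 complete children it ran with 4 − 1 = 3 and (8 − 1) × 3 = 21 degrees of freedom.

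**Recordings discarded, by time of leaving:**

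| All 8 leave | Valid recordings each | Discarded |
|---|---|---|
| before week 4 | 1 | 8 |
| between weeks 4 and 6 | 2 | 16 |
| after week 6 | 3 | 24 |

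A child with only a baseline recording says little about change under any method, so the first row is a small loss.

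**Precision with random drop-out.** SE of a week 0 to 4 change = SD × √(2/n).
- All 20 children: 0.15 × √(2/20) = 0.047.
- 16 completers: 0.15 × √(2/16) = 0.053.
- Ratio: √(20/16) = 1.118, about 12% wider. This holds if all 20% leave after week 4.
- If half of the drop-outs leave before week 4, 18 pairs exist and 16 are used: √(18/16) = 1.061, about 6% wider.
- For a sequence group of 10 the SEs are 0.15 × √(2/10) = 0.067 and 0.15 × √(2/8) = 0.075, with the same 12% ratio.

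**Bias if drop-out depends on observed change.** Assumptions, not in the protocol: true week 0 to 4 gain 0.20; drop-out after week 4 follows a logistic model in the observed gain, with slope 0.7 to 1.5 per SD of gain (SD of gain = 0.15 × √2 = 0.212). Mean gain among completers:

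| Leaving after week 4 | Slope 0.7 | Slope 1.5 |
|---|---|---|
| 10% | 0.214 | 0.225 |
| 20% | 0.228 | 0.247 |
| 30% | 0.242 | 0.270 |

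At 20% the excess is 0.028 to 0.047. That is 0.6 to 1.0 SE with 20 children (SE 0.047), or 0.4 to 0.7 SE with a sequence group of 10 (SE 0.067). With random drop-out it is zero.

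An extreme case can be checked by hand. If the 20% with the smallest gain leave, the completer mean is 0.20 + 0.212 × 0.280/0.80 = 0.274, where 0.280 is the normal density at the 20th percentile.

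**Can the discarded data correct this?** In the settings above, the mean over all 20 week 0 to 4 pairs is 0.20 by construction, so it tests nothing. The informative check is week 10, where leavers have no value. Assume the same gain at weeks 4 and 10, a return to baseline at week 6, and an SD of individual response from 0 to 0.15. Completers then show 0.22 to 0.23 at week 10 if the odds of leaving triple per SD of poorer week 4 change, and 0.24 to 0.26 if the worst 20% leave. An estimate that uses leavers' weeks 0 and 4 returns 0.20 in every setting.

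**The case against.** **Other named tests keep these children.** This stands. The Wilcoxon test compares start and end of treatment, so a child who leaves after week 4 still supplies the period 1 pair. A reader might infer that every estimate of change from baseline becomes one for completers only; the protocol does not support that.

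**The treatment comparison is untouched.** This also stands. The primary objective compares tPCS with Melatonin, and independent t-tests do not need four recordings. A reader might infer that unequal drop-out between treatments would bias the treatment effect through this ANOVA, but no treatment contrast comes from a within-group analysis. Nor is planned power lost: 32 completers are what section 8.1 provides for.

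**The size of the bias is assumed.** This stands. The 0.2 in section 8.1 is a difference between treatments, so using it as a child's gain is only illustrative. Section 2.5 speaks of tolerability and withdrawal, not poor sleep response, and selection on one need not be selection on the other. A flat statement that the change will be overstated is not supported.

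**Missing-data rules belong in the SAP, and imputation is not excluded.** The absence of such a rule is indeed no finding. The point is narrower: section 8.2 names a method that, used as named, excludes incomplete children.

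**A mixed model with time and treatment alone would be incomplete.** Correct. Within a sequence group, time and treatment are confounded, and carryover could enter the week 6 and period 2 values. A group-by-time interaction answers this for a within-group description, because each group keeps its own mean at each time point.

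**Conclusion.** The point holds for one supporting analysis: within-group change across the four time points. The exclusion of incomplete children follows from the named method, and at the expected drop-out it discards 8 to 24 valid recordings. The certain cost is precision, at most about 12% in the SE of a week 0 to 4 change, and less the earlier children leave. Bias is conditional: none if drop-out is random; about 0.23 to 0.25 for an assumed true gain of 0.20 if all 20% leave after week 4 in relation to their observed gain; smaller with earlier drop-out. It is worth correcting because the remedy is cheap, but it does not threaten the primary comparison.

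**What to change.** In section 8.2, replace the one-way repeated-measures ANOVA with a linear mixed model (MIXED in the SPSS software already named). Include categorical time point, sequence group and their interaction, with either a within-child covariance matrix or a random child effect, and use every available recording from all randomised children. An unstructured covariance is preferable if it converges, because a random child effect alone imposes equal correlation between all time points. Report the within-group time contrasts from this model, and keep the complete-case ANOVA as a sensitivity analysis.

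The cost is a sentence or two in section 8.2, with the same software and data and no added burden on families. The downside is small: the model relies on missingness depending only on observed values. That is an assumption, but a weaker one than the complete-case ANOVA makes, namely that completers represent all randomised children.

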9 DIRECT ACCESS TO SOURCE DATA/DOCUMENTS

The investigator(s)/institution(s) will permit study-related monitoring, audits and/or IRB review and regulatory inspection(s), providing direct access to source data/document.

10 QUALITY CONTROL AND QUALITY ASSURANCE

The principal investigator will ensure adherence with the protocol and accuracy in relation to data entry. Quality of the data will be ensured and monitored every month during the study period.

The investigator will maintain essential study documents (protocol and amendments, source documentation, relevant correspondence, and all other supporting documentation) in a confidential manner as required by the approving ethics committee.

11 ETHICAL CONSIDERATIONS

This study will be conducted in accordance with the ethical principles that have their origin in the Declaration of Helsinki and that are consistent with the Good Clinical Practice and the applicable regulatory requirements.

This final Clinical Trial Protocol, including the final version of the Participant Information Sheet and Consent Form, must be approved in writing by the Centralised Institutional Review Board (CIRB) and regulatory approval from Health Sciences Authority (HSA), prior to enrolment of any patient into the study.

The principal investigator is responsible for informing the CIRB and HSA of any amendments to the protocol or other study-related documents, as per local requirement.

11.1 Informed Consent

In obtaining and documenting informed consent, the investigator will comply with the GCP guidelines and to the ethical principles that have their origin in the Declaration of Helsinki. Potential participant will be identified by therapist or doctor in KKH/and if inclusion criteria met, consent will be signed in the presence of a witness. Consent taking will take place in the clinic room or rehab outpatient room. The study investigator will sign the consent and make sure that study information is correctly given to the study participant.

If the child has some but not full understanding of the Participant Information Sheet & Consent Form (attached to Section P6), (aged 6 and above), the simplified version (i.e. Child/ Participant Assent Form) will be used. If the child aged 13 and above, has sufficient understanding of the Participant Information Sheet & Consent Form, he will sign it with the parent co-signing in the legal guardian section.

11.2 Confidentiality of Data and Patient Records

All data will be entered into a secure password-protected document in the desktop. Identifiable patient data will be anonymised. Access to the data will only be open to the study investigators. Hardcopy of the data forms will be stored in a locked cupboard in the department.

12 PUBLICATIONS

Following approval by CIRB, the study will be registered on ClinicalTrials.Gov by the Principal Investigator. Study results will be published in peer-reviewed scientific literature regardless of the trial's

outcome. The CONSORT 2010 Statement will be adhered to in publication of study findings to ensure that international standards of authorship and publication are met.

13 RETENTION OF TRIAL DOCUMENTS

When the study is completed, the research data will be kept in a secure password-protected document in the desktop at the department. All the documents will be retained for at least 7 years after completion of the research study.

14 FUNDING and INSURANCE

FUNDING AND RESOURCES

In cash:

Item	Total
Actigraphy (\$2600 x 2)	\$5,600
Travel allowance 40 subjects x \$50	\$2,000
Melatonin (\$25 for 70s) x 72 bottles	\$1,800
Research Coordinator (0.1 FTE x 2 years)	\$12,000
IRB application	\$800
Presentation at overseas conference	\$3,200
Total	\$25,000

In-kind contributions:

KKH will supply the manpower for recruitment of study subjects and carrying out objective assessments and questionnaires for the study subjects.

Ascenzion will supply up to 8 tPCS units and the manpower for carrying out the tPCS for the participants during the study period.

REFERENCES

ⁱ Marriner A, Pestell C, Bayliss D, McCann M, Bucks R. Confirmatory factor analysis of the Sleep Disturbance Scale for Children (SDSC) in a clinical sample of children and adolescents. *J Sleep Res* 2017;26:587-94.

ⁱⁱ Romeo DM, Brogna C, Musto E, et al. Sleep disturbances in preschool age children with cerebral palsy: a questionnaire study. *Sleep Med* 2014;15:1089-93.

ⁱⁱⁱ Newman C, O'Regan M, Hensey O. Sleep disorders in children with cerebral palsy. *Dev Med Child Neurol*. 2006; 48:564-8. [PubMed: 16780625]

^{iv} ZM Ng, JB Lin, PC Khoo, VS Rajadurai, DWS Chan, HT Ong, J Wong, CT Choong, KW Lim, KBL Lim, TH Yeo. Causes, functional outcomes and healthcare utilisation of people with cerebral palsy in Singapore. *Ann Acad Med Singap* 2021;50:111-8

^v Mol EM, Monbaliu E, Ven M, Vergote M, Prinzie P. The use of night orthoses in cerebral palsy treatment: sleep disturbance in children and parental burden or not? *Res Dev Disabil* 2012; 33:341-9.

^{vi} *Sleep Med*. 2011 March ; 12(3): 252–256. doi:10.1016/j.sleep.2010.07.019.

^{vii} Zhou Q, Yu C, Yu H, Zhang Y, Liu Z, Hu Z, Yuan TF, Zhou D. The effects of repeated transcranial direct current stimulation on sleep quality and depression symptoms in patients with major depression and insomnia. *Sleep Med*. 2020 Jun;70:17-26. doi: 10.1016/j.sleep.2020.02.003. Epub 2020 Feb 20. PMID: 32179428.

